5.2.2 Study Drug: Vorinostat (ZOLINZA[®])

Treatment can be administered on an outpatient basis. Subjects will take 400 mg orally once daily with food.

Vorinostat is approved for marketing in the US, Japan and Australia and is indicated for the treatment of progressive, persistent or recurrent CTCL. Investigators will administer according to the currently approved US prescribing information (e.g. dosage and administration, warnings, precautions, adverse reactions, dose modifications and omissions and storage information). No other investigational or commercial agents or therapies other than the study treatments and those described in Section 5.4.1 may be administered with the intent to treat the subject's malignancy.

5.2.2.1 Definition of Treatment Cycle

Each treatment cycle is 28 days.

5.2.2.2 Delays in Dosing

Refer to Section 5.2.2.5.

5.2.2.3 Duration of Treatment

Subjects may remain in the treatment phase up until PD, drug intolerance or unacceptable toxicity, or until any of the other criteria for study removal are met, as defined in Section 5.5. Except in cases of unacceptable toxicity or drug intolerance, every effort should be made to ensure the subject remains in the study until disease progression (See Section 7.2.4, regarding definition of disease progression).

At each cycle, the investigator must minimally have reviewed the mSWAT to determine if progression of skin disease has occurred prior to subsequent dosing. Ideally, results of flow cytometry and CT assessment, as applicable, should be reviewed at this visit as well. However, it is understood that these results may not be reported for several days and may not be available. Once those results are obtained evidence of progression in all compartments should be determined.

In cases where the definition of PD or relapse is met but the clinical impression is questionable, subjects may remain on study until the next evaluation (4 weeks later if questionable finding in skin or blood; 8 weeks later in first year and 16 weeks later after Year 1 if questionable finding in lymph nodes or viscera, with at least stable disease in other compartments) to avoid a subject being removed prematurely from the study. If PD is confirmed at this subsequent evaluation, subject should be discontinued from treatment. If PD is not confirmed at this subsequent evaluation, the subject may remain on study.

This course of action only applies to cases where the clinical impression is questionable; subjects in frank or obvious PD in any compartment should be discontinued from protocol therapy.

If clinical progression is noted at any time prior to the scheduled assessments for efficacy, the assessments (CT, mSWAT, skin photographs and flow cytometry) should be done at that time to fully document disease progression. CT must be performed even if previously negative at baseline.

If the subject experiences an overall CR, the subject may continue treatment for up to 12 months or until progression, whichever comes first.

For subjects who are continuing to receive study treatment at the time of the primary efficacy analysis, procedures and assessments are described in Section 7.7.

5.2.2.4 Replacement of Subjects

Subjects will not be replaced.

5.2.2.5 Dose Modifications

Management of severe or intolerable adverse reactions may require dose omission, reduction or interruption of vorinostat therapy. Refer to US prescribing information for complete recommendations regarding dose modifications.

5.3 Cross-over to Study Drug KW-0761

Subjects who have received 2 full treatment cycles and demonstrate progression of disease on treatment with vorinostat at the 8 week (Cycle 2, Day 26-28) assessment, or anytime thereafter, may cross over to treatment with KW-0761 after discussion with Medical Monitor or designee and receipt of approval for cross over from KKD. Investigators should strive to maintain subjects on treatment for at least the 8 week period, adjusting the dose of vorinostat as needed for toxicities in order to allow sufficient time to see effect. In cases where a subject's disease progresses rapidly (i.e., prior to 8 weeks), the Medical Monitor or designee should be contacted and may consider the possibility of early crossover, if appropriate for that subject. All subjects must undergo the full extent of disease evaluations (including CT scanning) to document PD prior to crossover.

There must be at least 2 weeks between the last dose of vorinostat and first dose of KW-0761. Subject must continue to meet eligibility criteria outlined in Section 3.4 and all toxicity must have resolved to Grade \leq 1 or to baseline in order to receive KW-0761. Treatment with KW-0761 should commence with procedures outlined for Day 1 in Table 1 of Study

Procedures for the first treatment cycle. In cases where a subject's disease progresses rapidly, the Medical Monitor or designee should be contacted and may consider initiation of treatment with KW-0761 prior to the 2-week washout period.

For subjects who are unable to tolerate the toxicities associated with vorinostat treatment, dose reduction should be initiated in an attempt to have the subject complete 2 full cycles of treatment. If the subject is unable to tolerate treatment with vorinostat despite attempts at dose reduction and has not had documented disease progression, the subject may receive KW-0761 after consultation with the Medical Monitor or designee and subsequent approval documentation from the Sponsor.

Drug intolerance is defined as:

- A serious AE attributed to the drug;
- \geq Grade 3 AEs excluding inadequately treated nausea, vomiting and diarrhea and alopecia.

5.4 Concomitant Therapy

Subjects should receive appropriate medical care for all intercurrent medical conditions consistent with community standards of medical care. Subjects are to receive vigorous supportive care for study medication-related toxicities and appropriate palliation for tumor symptoms, such as pain and anorexia.

All concomitant treatments whether for treatment of concurrent medical conditions, toxicity, management of pain, infections or other complications of the malignancy, must be recorded on the relevant electronic case report form (eCRF) page along with the reason for use.

Medication taken within 30 days prior to the first dose of study drug, and at any time after the start of treatment until 30 days after the final study drug administration will be recorded. A medication taken during follow-up will also be recorded if it is used to treat an AE or is temporally associated with an AE and may have a causal relationship.

While on study treatment, subjects are not permitted to receive any experimental therapy or anticancer therapy other than the study medication. Any subject requiring other anticancer therapy is to be removed from study treatment.

5.4.1 Permitted Treatment

- Hematopoietic growth factors and erythropoiesis-stimulating agents (based on threshold and target hemoglobin levels in the American Society of Hematology (ASH)/American Society of Clinical Oncology (ASCO) guidelines) (Rizzo, 2010) are allowed, if consistent with regional approved prescribing information, after completing Cycle 1.

- Subjects on a stable dose of a low dose systemic corticosteroid (≤ 20 mg prednisone equivalent) for at least 4 weeks prior to the Pre-treatment Visit may continue use. Subjects may receive intra-articular corticosteroid injections, intraocular corticosteroids drops, inhalation or nasal corticosteroids and replacement doses of systemic corticosteroids as needed.
- Subjects on a stable dose of medium or low potency topical corticosteroids for at least 4 weeks prior to the Pre-treatment Visit may continue use at the same dose, although the investigator should attempt to taper the use to the lowest dosage tolerable while on study.
- Prophylactic treatment for the infectious complications of T-cell lymphoma is permitted at the discretion of the investigator.
- For subjects receiving vorinostat, prolongation of prothrombin time (PT) and International Normalized Ratio (INR) have been observed in subject receiving concomitant therapy with coumarin-derivative anticoagulants, carefully monitor PT and INR in these subjects.
- Influenza vaccination consisting of killed virus or viral particles may be administered to subjects on study. Subjects should not receive an influenza vaccine containing live attenuated virus. It should also be understood that because KW-0761, as well as CTCL, can affect the immune system, immunity to influenza may not be achieved despite vaccination.

5.4.2 Prohibited Treatment

- Initiation of treatment with systemic steroids or increase in dose while on study is not permitted except to treat an infusion reaction (see Section 5.2.1.7). Subjects who require systemic steroid therapy to treat a severe skin rash should be discontinued from the study (see Section 5.2.1.8).
- Initiation of treatment with topical corticosteroids while on study is not permitted except to treat an acute rash.
- Any experimental therapy or anticancer therapy including radiation and phototherapy other than the study medications.
- Any live or live attenuated vaccine.
- Alternative medicines, particularly use of St. John's Wort.
- Immunomodulatory agents such as methotrexate; azathioprine; iv immunoglobulin; cyclophosphamide; cyclosporine; mycophenolate; infliximab; etanercept; leflunomide; adalimumab; lenalidomide; abatacept; rituximab; anakinra; interferon- α ; interferon- β ; IL-2 and natalizumab.
- Other concurrent HDAC inhibitors including valproic acid.
- Whenever possible, concomitant use of drugs which may cause a prolongation of the QTc interval should be avoided. If such a drug is necessary (e.g., anti-emetics), monitor the QTc interval closely.

5.5 Criteria for Removal from Study

In the absence of a medical contraindication or significant protocol violation, every effort will be made by the Principal Investigator to keep the subject in the study. However, should the subject decide to discontinue treatment, all efforts will be made to complete and report the observations as thoroughly as possible, including a complete final evaluation at the time of the subject's withdrawal with an explanation of why the subject is withdrawing from the study.

Study treatment will be stopped if any of the following events occur:

- Disease progression (as defined in Section 7.2.4);
- An infusion-related reaction (see Section 5.2.1.7);
 - with a severity of \geq Grade 2 upon re-challenge with KW-0761,
 - with a severity of Grade 3 with symptoms that do not abate after 30 minutes,
 - with a severity of Grade 4,
 - requiring the administration of systemic vasopressors,
 - that results in hospitalization (directly due to infusion reaction symptoms),
- Initiation of treatment with systemic corticosteroids, except when initiated to treat an infusion reaction (see Section 5.2.1.7);
- A true hypersensitivity (i.e., allergic) reaction to KW-0761 with a severity of \geq Grade 2;
- A rash which recurs and becomes Grade 3 on re-challenge (see Section 5.2.1.8);
- A rash which recurs at Grade 2 or higher for a third time on re-challenge (see Section 5.2.1.8);
- A rash which requires systemic steroid therapy (see Section 5.2.1.8);
- Confirmed SJS/TEN (see Section 5.2.1.8);
- The subject has any clinical AE, laboratory abnormality, intercurrent illness, or other medical condition that indicates to the Investigator that continued participation is not in the best interest of the subject. The Investigator should make a distinction between AEs that may require only interruption of study medication and those that require discontinuation;
- The subject wishes to withdraw consent from the study in the absence of a medical need to withdraw as determined by the Investigator;
- The Investigator concludes that it is in the best interest of the subject to discontinue study treatment including subjects who have not benefited from treatment;
- Subject is willingly or inadvertently noncompliant in the opinion of the Investigator;
- Administrative reasons determined by the Sponsor; or
- If pregnancy is suspected while the subject is receiving study treatment, the study medication must immediately be withheld until the result of pregnancy testing is known.

If pregnancy is confirmed, the study medication will be permanently discontinued and the subject withdrawn from treatment.

In the case of pregnancy that occurs while the subject is receiving study medication through 6 months after the last dose of study medication, the Investigator must immediately notify the Sponsor of this event and record the pregnancy on the Pregnancy Surveillance Form. The Sponsor must also be notified if a partner of a study subject becomes pregnant while the subject was receiving study medication through 6 months after the last dose of study medication. Reasonable attempts will be made to follow the pregnancy to conclusion in order to obtain information regarding the outcome.

The Investigator must complete all applicable End-of-treatment visit procedures (i.e., safety laboratory parameters, electrocardiogram (ECG), physical examination, vital signs) and eCRF pages for subjects who discontinue treatment, and include the reason for discontinuation of treatment.

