
erythematosus; rheumatoid arthritis; Crohn’s disease; psoriasis).
 
10) Is pregnant (confirmed by beta human chorionic gonadotrophin [β-HCG]) or lactating.
 
Prohibited Therapies and/or Medications
 
11) Prior treatment with KW-0761.
 
12) Prior treatment with vorinostat. Patients who were exposed to vorinostat for a short time, did not progress while on treatment, and did not have intolerable toxicity but were discontinued for another reason (e.g., comorbidity) may be permitted to enter the study after discussion with the Medical Monitor.
 
13) Have had any therapy directed against the subject’s underlying cancer or any investigational medications within four weeks of randomization (skin directed treatments, including topicals and radiation within 2 weeks of randomization). However, subjects with rapidly progressive malignant disease may be enrolled prior to this period after discussion with the Medical Monitor.
 
14) Subjects on a stable dose of a low dose systemic corticosteroid (≤ 20 mg prednisone equivalent) for at least 4 weeks prior to the Pre-treatment Visit may continue use although the investigator should attempt to taper the use to the lowest dosage tolerable while on study. Initiation of treatment with systemic corticosteroids or increase in dose while on study is not permitted except to treat an infusion reaction (see Section 5.2.1.7). Subjects may receive intra-articular corticosteroid injections, intraocular corticosteroid drops, inhalation or nasal corticosteroids and replacement doses of systemic corticosteroids as needed.
 
15) Subjects on a stable dose of medium or low potency topical corticosteroids for at least 4 weeks prior to the Pre-treatment Visit may continue use at the same dose, although the investigator should attempt to taper the use to the lowest dosage tolerable while on study. Initiation of treatment with topical corticosteroids while on study is not permitted except to treat an acute rash.
 
16) History of allogeneic transplant.
 
17) Autologous hematopoietic stem cell transplant within 90 days of the Pre-treatment Visit.
 
18) Subjects on any immunomodulatory drug for concomitant or intercurrent conditions other than T-cell lymphoma or who have received any of these agents within 4 weeks of treatment, including but not limited to the following, will be excluded: low dose or oral methotrexate; azathioprine; intravenous (iv) immunoglobulin; low dose or oral cyclophosphamide; cyclosporine; mycophenolate; infliximab; etanercept; leflunomide; adalimumab; lenalidomide; abatacept; rituximab; anakinra; interferon-β; IL-2 and natalizumab.
		

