- 9) Known active autoimmune disease will be excluded. (For example, Graves' disease; systemic lupus erythematosus; rheumatoid arthritis; Crohn's disease; psoriasis).
- 10) Is pregnant (confirmed by beta human chorionic gonadotrophin [β -HCG]) or lactating.

Prohibited Therapies and/or Medications

- 11) Prior treatment with KW-0761.
- 12) Prior treatment with vorinostat. Patients who were exposed to vorinostat for a short time, did not progress while on treatment, and did not have intolerable toxicity but were discontinued for another reason (e.g., comorbidity) may be permitted to enter the study after discussion with the Medical Monitor.
- 13) Have had any therapy directed against the subject's underlying cancer or any investigational medications within four weeks of randomization (skin directed treatments, including topicals and radiation within 2 weeks of randomization). However, subjects with rapidly progressive malignant disease may be enrolled prior to this period after discussion with the Medical Monitor.
- 14) Subjects on a stable dose of a low dose systemic corticosteroid (≤ 20 mg prednisone equivalent) for at least 4 weeks prior to the Pre-treatment Visit may continue use although the investigator should attempt to taper the use to the lowest dosage tolerable while on study. Initiation of treatment with systemic corticosteroids or increase in dose while on study is not permitted except to treat an infusion reaction (see Section 5.2.1.7). Subjects may receive intra-articular corticosteroid injections, intraocular corticosteroid drops, inhalation or nasal corticosteroids and replacement doses of systemic corticosteroids as needed.
- 15) Subjects on a stable dose of medium or low potency topical corticosteroids for at least 4 weeks prior to the Pre-treatment Visit may continue use at the same dose, although the investigator should attempt to taper the use to the lowest dosage tolerable while on study. Initiation of treatment with topical corticosteroids while on study is not permitted except to treat an acute rash.
- 16) History of allogeneic transplant.
- 17) Autologous hematopoietic stem cell transplant within 90 days of the Pre-treatment Visit.

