7.2 Efficacy Evaluations

Response in skin and blood will be evaluated every 4 weeks during treatment. In the first year of treatment, response in lymph nodes and viscera will be documented at 4 weeks after the start of study treatment (end of Cycle 1) and every 8 weeks thereafter. After the first year, response in the lymph nodes and viscera will be documented every 16 weeks. In the first year of treatment, the global composite response (including skin, blood, lymph nodes and viscera) will be assessed at 4 weeks (end of Cycle 1) and every 8 weeks thereafter (Cycle 3, 5, etc.); after the first year, global composite response will be assessed every 16 weeks (Cycle 17, 21, etc.).

For those subjects who cross over from the vorinostat arm to KW-0761 treatment, response within the second arm of the study will be measured from the first day of dosing with KW-0761. Baseline measurements for this arm are considered to be those taken at the last assessment which documented progression on vorinostat or if repeated, assessment completed closest to and before the first KW-0761 infusion (i.e., mSWAT done on Cycle 1, Day 1 is the new baseline).

Prior to starting study treatment, visual inspection of the skin with photographs and measurements (mSWAT), assessment of CT images and hematological examinations will be done to document extent of disease. Skin disease will be evaluated using a modification of the SWAT (Olsen, 2007; Stevens, 2002). Response for skin will be based on mSWAT scores. In addition, pruritus will be evaluated using a Likert scale and Itchy QoL. Lymph nodes and visceral disease will be evaluated by CT. The response in blood will be assessed by flow cytometry.

The response in all compartments (skin, blood, lymph nodes and viscera, as applicable) and overall response will be assessed, except as otherwise noted, in accordance with the response criteria determined by consensus of the International Society of Cutaneous Lymphomas (ISCL), the United States Cutaneous Lymphoma Consortium (USCLC) and the Cutaneous Lymphoma Task Force of the European Organization for Research and Treatment of Cancer (EORTC) (Olsen, 2011).

If clinical progression is noted at any time prior to the scheduled assessments for efficacy, the assessments (CT, mSWAT, skin photographs and flow cytometry) should be done at that time to fully document disease progression. CT must be performed even if previously negative at baseline.

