7.5 Follow-Up

All subjects will be contacted by telephone every 30 days (± 7 days) up to 90 days after the last dose of study medication or initiation of alternative therapy, whichever comes first, to confirm any new onset AEs or toxicities. If a subject who has received KW-0761 undergoes a stem cell transplant at any time during or after the 90-day follow-up period, AEs/SAEs should be documented from the transplant procedure through 180 days post-transplant.

During follow-up, medications used to treat an AE and those that are temporally associated with the AE and may have a causal relationship will be recorded. In all subjects who cross

over from vorinostat to KW-0761, the causality should be assessed for both drugs for 30 days after vorinostat was stopped (or later if the event is considered to be related to vorinostat).

- After a subject who receives KW-0761 goes off study, if CD4 and CD8 counts are less than $200/\text{mm}^3$ at the End-of-treatment visit, they will be followed every 3 months (± 14 days) until they return to at least $200/\text{mm}^3$, initiation of alternative therapy or 1 year, whichever comes first.
- In the absence of disease progression, all subjects or their referring physicians will be contacted every 3 months (± 14 days) until documented disease progression or death, or initiation of alternative therapy.
- All subjects or their referring physician will be contacted every 3 months (± 14 days) to ascertain survival status.
- For all subjects who have received KW-0761, subsequent stem cell transplant information should be recorded in a separate CRF provided by the Sponsor. For subjects who undergo transplant, concomitant medications and AEs/SAEs should be documented through 180 days post-transplant on the CRFs provided.
- All follow up information and attempts to obtain follow up information should be documented in the subject's source record.

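### Section 5.5 stops treatment for any newly started systemic corticosteroid other than for an infusion reaction, although Section 5.4.1 permits replacement doses as needed

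*Protocol*

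**What the plan says.** Four places in the protocol deal with systemic corticosteroids during treatment.

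- **Section 5.5** (removal from study) gives a list of events, any one of which requires study treatment to be stopped. One item reads "Initiation of treatment with systemic corticosteroids, except when initiated to treat an infusion reaction (see Section 5.2.1.7". Steroids for rash are a separate item.
- **Section 5.4.2** (prohibited treatment) says "Initiation of treatment with systemic steroids or increase in dose while on study is not permitted except to treat an infusion reaction".
- **Section 5.4.1** (permitted treatment) allows "inhalation or nasal corticosteroids and replacement doses of systemic corticosteroids as needed".
- **Section 3.3, exclusion criterion 14**, repeated in the synopsis, states the ban on initiation or dose increase and follows it at once with the permission for "replacement doses of systemic corticosteroids as needed". It also says that subjects on a stable low dose at entry "may continue use although the investigator should attempt to taper the use to the lowest dosage tolerable while on study".

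Section 5.5 cross-refers to 5.2.1.7 for infusion reactions. It does not refer to 5.4.1.

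**The concern.** The same act, starting a replacement dose of systemic corticosteroid on study, is allowed by 5.4.1, forbidden by 5.4.2 and a compulsory stop under 5.5. A site cannot follow all three. One site may give the replacement dose and continue treatment; another may stop treatment because 5.5 leaves it no choice.

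The need is foreseeable. Criterion 14 asks investigators to try to taper existing systemic steroid, and a subject tapered off completely may later need replacement.

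At stake for that subject is the loss of randomized therapy because of a medicine the protocol permits. For the data, the stop is an event for time to treatment failure (TTF), and the subject may leave the on-treatment assessment schedule. Subjects already on replacement steroid at entry are not affected, because the trigger is initiation.

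**Working it through.** **Step 1: the rules side by side.** The question is what each section requires for a subject who was not on systemic steroid and now starts a replacement dose.

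| Section | Rule | Exceptions stated | Result for this subject |
|---|---|---|---|
| 5.4.1 | Replacement doses allowed as needed | – | Permitted |
| 3.3, criterion 14 | Initiation or increase banned; next sentence allows replacement doses | Infusion reaction, then replacement by the adjacent sentence | Permitted, reading the two sentences together |
| 5.4.2 | Initiation or increase banned | Infusion reaction only | Prohibited |
| 5.5 | Stop treatment on initiation | Infusion reaction only | Treatment must stop |

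Section 5.4.1 itself describes replacement doses as systemic corticosteroids, the same term that 5.5 uses. The permission is not limited to use that began before entry. The conflict is therefore in the text. No power, alpha or event calculation depends on it.

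**Step 2: effect on endpoints.** SAP 6.11.1.4.2 counts discontinuation of randomized treatment for any reason as a TTF event, except stopping after one year on treatment with a complete response (CR). A stop under this item is thus a TTF event, usually an earlier one rather than an additional one. SAP 6.11.2.5 treats TTF as exploratory. The stop is not itself a progression-free survival (PFS) event. Under SAP 6.11.1.1, progression documented in follow-up still counts for primary PFS.

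**Step 3: change in observation for a subject not in CR.** On treatment, Section 7.2 says "Response in skin and blood will be evaluated every 4 weeks during treatment". Nodes, viscera and the global score are assessed at the end of Cycle 1 and then every 8 weeks in year 1; "After the first year, response in the lymph nodes and viscera will be documented every 16 weeks". After a stop, Section 7.5 says "In the absence of disease progression, all subjects or their referring physicians will be contacted every 3 months", with a window of 14 days either way.

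Three months = 3 × 365.25 / 12 = 91.3 days. With the window: 91.3 − 14 = 77.3 to 91.3 + 14 = 105.3 days.

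| On-treatment interval | Contact interval ÷ on-treatment interval | Range with the window |
|---|---|---|
| Skin and blood, 28 days | 91.3 / 28 = 3.26 | 77.3 / 28 = 2.76 to 105.3 / 28 = 3.76 |
| Nodes, viscera, global score, year 1 after Cycle 1, 56 days | 91.3 / 56 = 1.63 | 77.3 / 56 = 1.38 to 105.3 / 56 = 1.88 |
| Nodes, viscera, global score, after year 1, 112 days | 91.3 / 112 = 0.82 | 77.3 / 112 = 0.69 to 105.3 / 112 = 0.94 |

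The ratios compare timing only. The follow-up item is a contact with the subject or referring physician, not a scheduled disease assessment, so the 0.82 does not mean that imaging is preserved.

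**Step 4: a subject who stops after CR.** Section 7.6 keeps mSWAT, CT, flow cytometry and overall response. These are due every 8 weeks (56 ± 14 = 42 to 70 days) for 6 months if CR came before one year on study, then every 16 weeks (112 ± 14 = 98 to 126 days). The loss of assessment in Step 3 does not apply.

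**The case against.** The best defence is that the intent is plain. Criterion 14 puts the ban and the permission in consecutive sentences, 5.4.1 comes just before 5.4.2 and 5.5, and a specific permission normally limits a general ban. Physiological replacement can also be read as falling outside treatment with steroids. Section 5.5 opens by asking for every effort to keep the subject in the study. This shows what was probably meant. It does not change what 5.5 and 5.4.2 say: neither carries the exception, and the protocol nowhere defines replacement as something other than treatment. Criterion 14 is an eligibility item, whereas 5.5 is the stopping rule.

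Other points stand in whole or part:

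- The taper example is narrow. The taper is to the lowest tolerable dose, and 5.5 is triggered by initiation, not by a dose increase. The example needs a subject tapered off fully who then restarts, and it assumes that restarting counts as initiation.
- The interval ratios apply to anyone who stops without progression or CR. They describe the consequence for one affected subject, not how often the problem occurs. Different handling by sites is a possibility, not an observed fact.
- The current text already covers the period of Amendment 10, when electronic data capture ends. A change now could do little for TTF data. It would still matter for treatment, because Sections 7.7 and 7.8 continue KW-0761 subject to the criteria in 5.5.

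**Conclusion.** The concern holds: the stopping rule in 5.5, and the ban in 5.4.2, contradict the permission in 5.4.1 and criterion 14. It is a minor correction. The documents do not say how many subjects would be affected; the number is probably small, and no estimate is offered. Alpha, power and the 255-event target are unchanged.

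The consequence for an affected subject is the loss of randomized treatment and a TTF event, normally earlier than it would otherwise have been. If the subject is not in CR, the interval for skin and blood is also about 3.3 times as long. This rests on reading 5.5 literally and on the need for replacement first arising on study.

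**What to change.** In Section 5.5, extend the exception in the systemic corticosteroid item so that it covers treatment of an infusion reaction (Section 5.2.1.7) *or use as replacement doses (see Section 5.4.1)*. Add the same replacement-dose exception to the ban in Section 5.4.2. Criterion 14 needs no change, and the separate items on steroids for rash stay as they are.

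The drafting cost is one clause in each of two places, with no new data, procedures or subjects. Because it is a protocol amendment, it needs the approvals in Sections 11.2 and 12.2, so it is best carried with another amendment.
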